### 4.4 DEMOGRAPHICS

Demographics (gender, age, age group, race, education, household purchase information) will be summarized in all consumers set population using descriptive statistics. Continuous demographic such as age will be summarized with continuous descriptive statistics: mean, standard deviation (SD), median, minimum and maximum. Categorical variables including gender, age group, and race will be analyzed using discrete summary statistics (frequency and percentage).

Listing of demographic information will be generated for full analysis set.

### 4.5 PRIMARY ANALYSES

Primary endpoints (defined in Section 2.1.1) will be analyzed individually in full analysis set, and no adjustment for multiple comparisons will be performed. The compliance rate

for each of the five primary endpoints will be reported and its two-sided 95% confidence limit will be computed by using the Clopper-Person exact method. The endpoint will have met the threshold for success if the lower bound of the 2-sided 95% exact confidence interval (CI) is at least 80%.

Listing of consumers for each of primary endpoints will be reported in full analysis set.

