7.2. Variables

7.2.1. Outcome definitions

Primary Endpoints

Primary endpoints are comprised of the proportion of consumers who comply with each of the 5 endpoints listed below:

- Consumer is 18 years of age or older
- Consumer does not exceed 2 sprays/nostril per day
- Dose is reduced to 1 spray/nostril per day if symptoms improve
- Doctor is consulted before use if a woman is pregnant or breastfeeding
- Doctor is consulted if symptoms do not improve after 7 days of use

Secondary Endpoints

Secondary endpoints are comprised of the proportion of consumers who comply with each of the specified endpoints listed below:

- Those taking HIV medications do not use the drug
- Doctor is consulted if medication is used more than 1 month *continuously*

Demographics and Profiling Information

Descriptive statistics will be used to report consumer demographics and additional profiling information. Demographic information is comprised of age, race, education and household purchase information (primary purchaser or other). The additional profiling information is comprised of the following:

- How long they have had allergies
- What type of allergies they have
- Typical allergy symptoms
- How often they see their doctor

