## 2. STUDY ENDPOINTS

### 2.1.1 Primary Endpoints

Primary endpoints are comprised of the proportion of consumers who comply with each of the five primary objective endpoints, namely:

1. Proportion of consumers with 18 years of age or older.
2. Proportion of consumers who don't exceed 2 sprays/nosetril per day.
3. Proportion of consumers whose dose is reduced to 1 spray/nosetril per day if symptoms improve.
4. Proportion of female consumers who consulted a Doctor before using the drug if pregnant or breastfeeding.
5. Proportion of consumers who consulted a Doctor if symptoms did not improve after 7 days of use.

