### 3. SAMPLE SIZE AND STATISTICAL POWER CONSIDERATIONS

1,537 consumers were planned to complete the survey. No targeting or enrichment for age, gender, and social backgrounds will be conducted. The demographics will be reported for those who choose to enter the online survey. For the threshold of 80% for success, this sample size of 1537 achieves at least 91% power with an assumed compliance rate of 83.3% for each of these five primary endpoints, and the significance level of 0.05 using a two-sided exact binomial test.

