#### 4.2.2 Full Analysis Set

The full analysis set is defined as all consumers who signed the Participation Agreement and did not answer “yes” to Q1A, Q1B, Q1C or left these questions blank.

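### Primary endpoints 3, 4 and 5 are conditional, but the plan sets no applicable-only denominator and no rule for scoring consumers outside the condition, while claiming 91% power on 1,537 for each

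*SAP*

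**What the plan says.** SAP 4.5 names one population for all five primary endpoints: "Primary endpoints (defined in Section 2.1.1) will be analyzed individually in full analysis set". An endpoint succeeds if the lower limit of its two-sided 95% Clopper-Pearson interval is at least 80%.

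SAP 4.2.2 builds that population from consent and screening answers only: "The full analysis set is defined as all consumers who signed the Participation Agreement and did not answer “yes” to Q1A, Q1B, Q1C" (blank answers are also mentioned). Whether a given direction applied to the consumer plays no part.

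The lead-in to SAP 2.1.1 is general: "Primary endpoints are comprised of the proportion of consumers who comply with each of the five primary objective endpoints". Protocol 7.2.1 is worded almost identically. Three of the items under it are conditional:

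- Endpoint 3: "Proportion of consumers whose dose is reduced to 1 spray/nosetril per day if symptoms improve"
- Endpoint 4: "Proportion of female consumers who consulted a Doctor before using the drug if pregnant or breastfeeding"
- Endpoint 5: "Proportion of consumers who consulted a Doctor if symptoms did not improve after 7 days of use"

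On size, SAP 3 and Protocol 7.4 say that "this sample size of 1537 achieves at least 91% power with an assumed compliance rate of 83.3% for each of these five primary endpoints".

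SAP 6 excludes missing data without imputation and does not mention answers that are not applicable. SAP 7 and 8 place derivation rules and table shells in separate documents.

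**The concern.** Endpoints 1 and 2 apply to every user of the product. Endpoints 3 to 5 do not: a woman who is neither pregnant nor breastfeeding has no consultation to make under endpoint 4, and a consumer who improved has none under endpoint 5. The compliance rate for such an endpoint has no meaning until the plan says who is in the denominator and what happens to everyone else.

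The plan names the full analysis set and a base of 1,537 but does not settle this. The choice is open for three of the five primary endpoints, and it can decide pass or fail by itself. The regulator required the study to learn how consumers follow the label. A pass on pregnancy consultation or on consultation after non-response could come from people whom the direction never concerned. Equally, a fail could arise because few consumers were in that situation.

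**Working it through.** **Inputs.** From the documents: N = 1,537, threshold 80%, assumed compliance 83.3%, two-sided alpha 0.05, exact binomial test (SAP 3) and the Clopper-Pearson lower-limit rule (SAP 4.5). The documents give no share of consumers to whom each condition applies. Every applicable number m below is an assumption, shown as a range.

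**The plan's own figure.** The lower limit for x of n is the 2.5% quantile of Beta(x, n − x + 1).

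- 1,260/1,537: lower limit 79.96%, fail.
- 1,261/1,537 (82.04%): lower limit 80.03%, pass.

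The pass mark is 1,261, which allows 1,537 − 1,261 = 276 failures (276/1,537 = 18.0%). Power = P(X ≥ 1,261 | n = 1,537, p = 0.833) = 0.9114. The stated 91% reproduces, with all 1,537 in the denominator.

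There are three ways to treat consumers outside the condition.

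**Reading A: scored compliant, base 1,537.** Compliers needed among the m applicable consumers = max(0, 1,261 − (1,537 − m)) = max(0, m − 276).

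| m (share) | Compliers needed | Needed rate |
|---|---|---|
| 46 (3%) | 0 | 0% |
| 154 (10%) | 0 | 0% |
| 276 (18.0%) | 0 | 0% |
| 307 (20%) | 31 | 10.1% |
| 461 (30%) | 185 | 40.1% |
| 768 (50%) | 492 | 64.1% |

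For example, suppose 46 women are pregnant or breastfeeding and none consults. The reported rate is (1,537 − 46)/1,537 = 1,491/1,537 = 97.0% (95% CI 96.0 to 97.8%), a pass. Among the women concerned it is 0/46 (0 to 7.7%). Restricting endpoint 4 to women does not cure this: with 800 women (assumed) the pass mark is 663, so 137 failures (17.1%) are still allowed.

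**Reading B: scored non-compliant, base 1,537.** The numerator cannot exceed m, so success is impossible unless m ≥ 1,261 (82.0%). With m = 768 and every one of them complying, 768/1,537 has a lower limit of 47.4%.

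**Reading C: left out, base m.** Power = P(X ≥ r | m, 0.833), where r is the smallest count whose lower limit reaches 80%.

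| m (share) | r | Power |
|---|---|---|
| 31 (2%) | 30 | 2.5% |
| 154 (10%) | 134 | 12.8% |
| 307 (20%) | 260 | 28.6% |
| 768 (50%) | 637 | 62.7% |
| 1,076 (70%) | 887 | 79.0% |
| 1,383 (90%) | 1,136 | 88.3% |
| 1,537 (100%) | 1,261 | 91.1% |

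When all m comply, the lower limit is 0.025^(1/m). This is 79.4% at m = 16 and 80.5% at m = 17, so below 17 applicable consumers success is impossible even with perfect compliance.

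**The case against.** A reader might infer that the plan counts consumers outside the condition as compliant, since that reading uses the full set and leaves an 83.3% rate attainable. The documents do not support this as a stated rule. SAP 4.5 names a population, not a scoring rule. The items in SAP 2.1.1, which SAP 4.5 adopts by reference, count actions taken (a dose reduced, a doctor consulted), and someone who had no reason to consult and did not consult is not naturally in that numerator. The conditional wording fits an applicable-only denominator at least as well. Nor is reading A the only one that uses 1,537, because reading B does too. This part of the objection stands, so the point is about an unset rule and not about a wrong rule.

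The derivation specifications and table shells are separate and not available, and they may contain the answer. The questionnaire is not available either, so skipped items might drop out as missing. That stands as a caution. However, Protocol 7.6 assigns the detailed methodology to the SAP, and the denominator of a primary endpoint belongs there. If those documents do use applicable-only denominators, the power statement is still wrong for endpoints 3 to 5 unless nearly everyone is applicable.

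Protocol 7.8.1 expects limited data on HIV medication, which might suggest that applicable-only denominators were intended throughout. This is weak evidence. Every respondent has used the product, so an applicable-only rate for that secondary endpoint would be 0% by construction.

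The result that zero compliance can pass is confined to conditions that apply to at most 18.0% of consumers. It does not carry over to a common condition, which symptom improvement may be. At 50% applicable, reading A still demands 64.1%.

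**Conclusion.** The concern holds as a specification gap with consequences, not as proof that the plan scores unaffected consumers as compliant. For endpoints 3, 4 and 5 the denominator and the handling of consumers outside the condition are unset, and none of the three readings makes the base of 1,537, the 80% rule and the 91% power sound together. Reading A can pass with no real compliance when at most 276 consumers are concerned. Reading B cannot pass with fewer than 1,261 concerned. Reading C measures the right quantity but, at 83.3% compliance, has 2.5% power at 31 applicable consumers and 62.7% at 768.

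The limits of 276, 1,261 and 17 follow from the plan's own rule; the first two also take all 1,537 as the base. The power figures rest in addition on assumed applicable numbers. The matter should be settled before analysis, because it affects the pass or fail result of three of the five primary endpoints.

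**What to change.** In SAP 2.1.1 and 4.5, set the denominators within the full analysis set:

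- Endpoint 3: consumers who report that symptoms improved.
- Endpoint 4: women who report being pregnant or breastfeeding when they used the product.
- Endpoint 5: consumers who report no improvement after 7 days of use.

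Class everyone else as not applicable, in neither numerator nor denominator, and keep this category separate from missing. Apply the 80% rule to these rates and print the applicable N beside each. Align the derivation specifications and table shells.

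In SAP 3 and Protocol 7.4, limit the 91% power claim to endpoints 1 and 2. For endpoints 3 to 5, give power or expected interval width over a range of applicable N, as in the reading C table.

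Protocol 7.6 calls for a protocol amendment for major modifications of the primary endpoint definition or its analysis. The sponsor should decide whether this change counts as one and, if so, amend Protocol 7.2.1 as well. No new data are needed provided the survey records each condition, which cannot be checked here. The price is wider intervals and a less favourable stated power for endpoints 3 to 5.

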#### **4.6 SECONDARY ANALYSES**

Secondary endpoints (defined in Section 2.1.2) will be analyzed individually in full analysis set, and no adjustment for multiple comparisons is performed. The compliance rate for each of the secondary endpoints will be reported and its two-sided 95% confidence limit will be computed by using the Clopper-Pearson exact method. There are no success thresholds set for secondary endpoints.

Listing of consumers for each of secondary endpoints will be reported in full analysis set.

#### **4.7 EXPLORATORY ANALYSES**

Descriptive summary will be provided for the following exploratory endpoints for the full analysis set, how long they have had allergies, what type of allergies they have, typical allergy symptoms, and how often they see their doctor.

Listing of consumers for exploratory endpoints above will be reported in full analysis set.

### **5. STATISTICAL SOFTWARE**

All statistical analyses will be performed using SAS 9.4 version.

### **6. HANDLING MISSING DATA**

The online survey will provide an audit trail so that data entry can be further reviewed or investigated, if needed. Programmed edit checks will be generated automatically, as the data is being entered into the system (e.g. the consumer will be restricted from proceeding in the survey until the previous question is answered). There will be no formal query resolution and no imputation for any missing data. Missing data will be excluded from the analysis.

### **7. PROGRAMMING SPECIFICATIONS**

The rules for programming derivations and dataset specifications are provided in separate database specification documentations.

## **8. MOCK TABLES, LISTINGS AND FIGURES (TLF)**

The study TLF shells will be provided in a separate document that will display content and format of all tables and listings in detail. There are no figures planned.
